## 6.2. Appendix 2 Data Derivations Rule

### 6.2.1. Study Day and Reference Dates

The reference day is defined as the day of 1st vaccine dose.

The study day is calculated as below:

- Assessment Date = Missing → Study Day = Missing
- Assessment Date < Reference Date → Study Day = Assessment Date – Ref Date
- Assessment Date ≥ Reference Date → Study Day = Assessment Date – Ref Date + 1

### 6.2.2. Assessment Window

Interval	Optimal length of interval 	Allowed interval
Visit 1→Visit 2	30-48 days	28-48 † days after Dose 1
Visit 2→Visit 3	30-48 days	28-48 † days after Dose 2
Visit 2→ESFU contact ‡	6 months	180-210 days after Dose 2

 Whenever possible the investigator should arrange study visits within this interval.

† Participants will not be eligible for inclusion in the Per Protocol Set for immunogenicity if they make the study visit outside this interval.

‡An extended safety follow-up (ESFU) contact (by telephone call or any other convenient procedure) to collect information on serious adverse events and medication taken for treatment of the same.

### 6.2.3. Handling of partial or missing Dates

Element	Reporting Detail			
General	
 
• Partial dates will be displayed as captured in participant listing displays.
 
• When partially completed dates (i.e. with missing day or month) are used in calculations, the following standard rules will be applied:           
 
- a missing day will be replaced by 15
 
- a missing day and month will be replaced by June 30th.
 
 
 
• Derivations for partial dates for Adverse Events, concomitant medication/medical history and age are detailed below
 
			
Adverse Events	
The general rules above apply, with the following exceptions for missing start day/ missing start day and month.
 
 
 Missing start day	If the event starts in the same month as at least 1 of the study doses, the contents of AE.AESTRPT (the flag indicating if the event occurred before or after vaccination) will be used to complete the date. If 'after vaccination' is selected, the imputed start date will	
 
		Missing start day	If the event starts in the same month as at least 1 of the study doses, the contents of AE.AESTRPT (the flag indicating if the event occurred before or after vaccination) will be used to complete the date. If 'after vaccination' is selected, the imputed start date will
Missing start day	If the event starts in the same month as at least 1 of the study doses, the contents of AE.AESTRPT (the flag indicating if the event occurred before or after vaccination) will be used to complete the date. If 'after vaccination' is selected, the imputed start date will			

Element	Reporting Detail	
		match the first (or only) study dose given during that month. If 'before vaccination' is selected, the imputed date will be 1 day before the first (or only) study dose given during that month.
	Missing start day and month	If the event starts in the same year as at least 1 of the study doses, the contents of AE.AESTRTPT (the flag indicating if the event occurred before or after vaccination) will be used to complete the date. If 'after vaccination' is selected, the imputed start date will match the first (or only) study dose given during that year. If 'before vaccination' is selected, the imputed date will be 1 day before the first (or only) study dose given during that year.
	Missing end day	The general rule is applied
	Missing end day and month	The general rule is applied
	Completely missing start/end date	No imputation
Concomitant Medications/Medical History	The general rules above apply.	
	Missing start day	The general rule is applied
	Missing start day and month	The general rule is applied
	Missing end day	The general rule is applied
	Missing end day and month	The general rule is applied
	Completely missing start/end date	No imputation

## 6.2.4. Handling of other missing data

### 6.2.4.1. Immunogenicity data

Missing immunogenicity data are not imputed.

### 6.2.4.2. Daily recording of solicited AEs

When a specific solicited AE is marked as having not occurred following a specific vaccination (i.e. SDTM CE.CEOCCUR=N for the specified post-vaccination period for the solicited AE in question), all daily measurements will be imputed as Grade 0.

When a specific solicited AE is marked as having occurred following a specific vaccination (i.e. SDTM CE.CEOCCUR=Y for the specified post-vaccination period for the solicited AE in question), any missing daily recordings will be given an imputed value which allows them to contribute to the 'Any' rows but not to specific grade rows of the solicited AE summary tables.

When the occurrence of a specific solicited AE is not present (i.e. SDTM CE.CEOCCUR is neither Y nor N for the specified post-vaccination period for the solicited AE in question) all missing daily recordings will be given an imputed value which allows them to contribute to the 'Any' rows but not to specific grade rows of the solicited AE summary tables.

The following table shows how solicited events are coded for intensity.

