9.4.1.2. Reactogenicity/Safety

Participants who missed reporting events (solicited/unsolicited AEs or concomitant medications) will be treated as participants without the events (solicited/unsolicited AEs or concomitant medications, respectively).

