#### 4.1.2. Reactogenicity

Participants without events (solicited/unsolicited AEs or concomitant medications) reported will be treated as participants without the events (solicited/unsolicited AEs or concomitant medications, respectively).

Refer to Section 6.2.4.2 for the intensity grading of solicited AEs.

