#### 4.5. Safety Analyses

The analyses will be descriptive and conducted on the ES.

The following calculations will be performed for each group:

- The percentage of doses and participants reporting at least 1 AE (solicited or unsolicited) during the 14-day (Day 1 to Day 14) solicited follow-up period will be computed, along with exact 95% CI. The same calculations will be done for AEs (solicited or unsolicited) rated as grade 3 in intensity and for AEs leading to a medically attended visit.
- The percentage of doses over the study and the percentage of participants (by dose and over the study) reporting each individual solicited systemic event will be computed, over the 14-day (Day 1 to Day 14) solicited follow-up period, following study intervention administration, along with exact 95% CI. The same calculations will be done for each individual solicited systemic event rated as grade 3 (grade 3 or grade 4 for fever) in intensity and events leading to a medically attended visit. Temperature above specific thresholds will also be summarized with threshold defined by half degree increment.

*Note: Intensity of fever will be assessed by considering the grading scales recommended by the Chinese authorities [NMPA 2019b].*

- The verbatim reports of unsolicited AEs will be reviewed by a physician and will be coded according to MedDRA. Every verbatim term will be matched with the appropriate Preferred Term. The percentage of participants with unsolicited AEs occurring within 31-day (Day 1 to Day 31) follow-up period after any dose with its exact 95% CI will be tabulated by Preferred Term. The same calculations will be done for each AE rated as grade 3 in intensity, for AEs leading to a medically attended visit and for AEs causally related to HRV as per the investigator assessment.
- The percentage of participants reporting the occurrence of SAEs (any, related, fatal, fatal related) from Dose 1 of the study intervention up to study end with its exact 95% CI will be tabulated by study group and by preferred term.
- The percentage of participants reporting the occurrence of SAEs (any, related, fatal, fatal related) within 31-day (Day 1 to Day 31) follow-up period after any dose with its exact 95% CI will be tabulated by study group and by preferred term.
- SAEs and drop outs due to AEs will be described in detail.

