## 4.8. Changes to Protocol Defined Analyses

There were no changes or deviations to the originally planned statistical analysis specified in the protocol (Dated: 13 May 2022).

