**Table 6      Intensity scales for solicited AEs – Attribution for codes for Diarrhea, Vomiting and Fever**

Event	Infant		
	Intensity grade (collected or measured)	Intensity grade (code attributed)	Parameter
Loss of appetite	0	0	Appetite as usual
	1	1	Eating less than usual/no effect on normal activity
	2	2	Eating less than usual/interferes with normal activity
	3	3	Not eating at all
Irritability/Fussiness	0	0	Behavior as usual
	1	1	Crying more than usual/no effect on normal activity
	2	2	Crying more than usual/interferes with normal activity
	3	3	Crying that cannot be comforted/prevents normal activity
Cough/runny nose	0	0	Normal
	1	1	Cough/runny nose which is easily tolerated
	2	2	Cough/runny nose which interferes with daily activity
	3	3	Cough/runny nose which prevents daily activity
Diarrhea	looser than normal stools/day	0	Normal (0-2 looser than normal stools/day)
		1	3 looser than normal stools/day
		2	4-5 looser than normal stools/day
		3	≥ 6 looser than normal stools/day
Vomiting	episodes of vomiting/day	0	Normal (no emesis)
		1	1 episode of vomiting/day
		2	2 episodes of vomiting/day
		3	≥3 episodes of vomiting/day
Fever †	Axillary Temperature (°C)	0	Normal (< 37.5°C)
		1	37.5°C – < 38.0°C
		2	38.0°C – < 39.5°C
		3	≥ 39.5°C
		4	≥ 39.5°C, lasts more than 5 consecutive days

†Axilla is the preferred route to measure temperature in China. If temperature is collected by other routes, the following conversion will be applied:

- Axillary temperature = oral temperature - 0.2°C;
- Axillary temperature = rectal temperature - 0.3°C.

The following table shows how participants contribute to each category for a specific solicited AE over the Day X to Day Y post-vaccination period:

Solicited AE category	Participants included in the calculation of the numerator
Any	All participants with at least 1 occurrence of the solicited AE at grade 1, grade 2, grade 3 or grade 4 between Day X and Day Y or with the solicited AE marked as present and at least 1 missing daily recording between Day X and Day Y
At least grade 1	All participants with at least 1 occurrence of the solicited AE at grade 1, grade 2, grade 3 or grade 4 between Day X and Day Y
At least grade 2	All participants with at least 1 occurrence of the solicited AE at grade 2, grade 3 or grade 4 between Day X and Day Y
At least grade 3	All participants with at least 1 occurrence of the solicited AE at grade 3 or grade 4 between Day X and Day Y

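### SAP 6.2.4.2 counts an unanswered solicited event with a missing diary day as 'Any', against its own numerator table, SAP 4.1.2 and protocol 9.4.1.2

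*SAP*

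**What the plan says.** SAP 6.2.4.2 sets three rules for daily solicited-event data, according to CEOCCUR. If it is no, every day becomes grade 0. If it is yes, missing days count in 'Any' but in no grade row. The third rule applies when "CE.CEOCCUR is neither Y nor N for the specified post-vaccination period", and there "all missing daily recordings will be given an imputed value which allows them to contribute to the 'Any' rows". Its operative wording is nearly identical to that of the rule for a confirmed event.

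The table that closes the section lists who enters each numerator. Apart from a recorded grade of 1 to 4, the only route into 'Any' is to be a participant "with the solicited AE marked as present and at least 1 missing daily recording between Day X and Day Y".

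Two general rules also bear on this:

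- SAP 4.1.2: "Participants without events (solicited/unsolicited AEs or concomitant medications) reported will be treated as participants without the events".
- Protocol 9.4.1.2: "Participants who missed reporting events (solicited/unsolicited AEs or concomitant medications) will be treated as participants without the events".

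On use and status, SAP 4.5 says "The analyses will be descriptive and conducted on the ES" and tabulates "the percentage of participants (by dose and over the study) reporting each individual solicited systemic event". SAP 4.8 says "There were no changes or deviations to the originally planned statistical analysis specified in the protocol".

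**The concern.** A blank CEOCCUR is not a mark that the event was present. The third rule nevertheless handles it like a confirmed event, while the table a few lines later leaves the same infant out of 'Any'. Nothing in the SAP ranks one above the other. If the third rule governs, it also departs from protocol 9.4.1.2, and SAP 4.8 does not declare that.

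The percentage of participants reporting each solicited event within 14 days of each dose is a secondary endpoint (protocol Section 3, Table 3). Followed literally, the third rule raises that percentage with infants for whom nobody reported an event. A diary never returned, with CEOCCUR blank throughout, would count as 'Any' for all six solicited events after that dose. Two programmers working from this one section could produce different tables from the same data.

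**Working it through.** **Where the rules differ.** Classify an infant, for one event and one dose, by CEOCCUR (yes, no, blank), by whether any grade of 1 or more is recorded, and by whether any day is missing. Leaving out the inconsistent case of CEOCCUR = no with a recorded grade gives 10 combinations. The imputation paragraphs and the numerator table disagree in exactly one. The four blank-field cases are:

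| Grade of 1 or more recorded | Day missing | 6.2.4.2, third rule | 6.2.4.2, table | SAP 4.1.2 and protocol 9.4.1.2 |
|---|---|---|---|---|
| no | no | not in 'Any' | not in 'Any' | no event |
| **no** | **yes** | **in 'Any'** | **not in 'Any'** | **no event** |
| yes | no | in 'Any' | in 'Any' | event |
| yes | yes | in 'Any' | in 'Any' | event |

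**Size of the effect.** The plan states no figure to reproduce. Inputs:

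- p, the true event rate per dose: assumed.
- m, the share of infants with a blank field and at least one missing day: assumed, and taken as unrelated to the event.
- 1000 infants per arm: protocol 9.2 and SAP Section 5, used only to convert percentages to counts.

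Formulas, with all exposed infants in the denominator:

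- Third rule: p(1−m) + m.
- Other rules: from p(1−m), if no true event among the m infants has a recorded grade, up to p, if all do.
- Gap: from (1−p)m to m.

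Per dose:

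| p | m | Third rule | Other rules | Gap (points) |
|---|---|---|---|---|
| 5% | 1% | 5.95% | 4.95% to 5.00% | 0.95 to 1.00 |
| 5% | 2% | 6.90% | 4.90% to 5.00% | 1.90 to 2.00 |
| 5% | 5% | 9.75% | 4.75% to 5.00% | 4.75 to 5.00 |
| 30% | 5% | 33.50% | 28.50% to 30.00% | 3.50 to 5.00 |

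For p = 5% and m = 2%: 0.05 × 0.98 + 0.02 = 0.069. The gap of 1.90 to 2.00 points is 19 to 20 infants per 1000.

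Over the study (two doses), p = 5% and m = 2% per dose:

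- Blank fields independent between doses: third rule 1 − (1 − 0.069)² = 13.32%; other rules 1 − (1 − 0.049)² = 9.56% up to 1 − 0.95² = 9.75%. Gap 3.57 to 3.76 points.
- Same 2% of infants blank at both doses, events independent: third rule 0.02 + 0.98 × 0.0975 = 11.56%; other rules 0.98 × 0.0975 = 9.56% up to 9.75%. Gap 1.8 to 2.0 points.

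**If blanks differ by arm.** Let the share of infants in the conflicting cell be 2% in one arm and 5% in the other, with a 20% rate among the rest in both (all assumed). The third rule gives 0.20 × 0.98 + 0.02 = 21.6% and 0.20 × 0.95 + 0.05 = 24.0%, a difference of 2.4 points produced by missing data. The table rule gives 19.6% and 19.0%, a difference of 0.6 points in the other direction.

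**The case against.** The strongest reply is that the texts work at different levels. The imputation paragraphs act on daily recordings and only allow a missing day to contribute; the table is the participant-level counting rule, comes later, and agrees with SAP 4.1.2 and the protocol. A programmer could reasonably follow the table. On that reading SAP 4.8 has nothing to declare. But the third rule would then be wrong text in an approved SAP, and a dataset derived from it could already carry the inflated flag when the table is applied. Reading the contribution to 'Any' as a denominator matter does not help either: the rule for CEOCCUR = yes uses the same words, and the table shows that there they mean the numerator.

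Several limits do stand:

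- The table only omits the infant from the numerator; the status of having had no event comes from SAP 4.1.2 and protocol 9.4.1.2.
- SAP 4.5 names the Exposed Set but does not spell out the per-dose denominator.
- Protocol 10.3.6 has diary cards verified with parents at Visits 2 and 3 and unreturned cards sought, so m may be small.
- The analyses are descriptive, and the row for at least grade 1 remains free of this imputation.
- Counting unknowns as events errs towards over-reporting reactogenicity, which a sponsor may prefer. That would be a legitimate choice if made openly and consistently.

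**Conclusion.** The contradiction holds, for infants with a blank CEOCCUR, at least one missing day and no recorded grade of 1 or more. For each event and dose, the 'Any' percentage differs between the rules by exactly the share of such infants. Neither that share nor the event rates are in the documents, so every size given here rests on assumed values. At m = 1% the gap is at most 1 point per dose. At p = 5% and m = 2% it is about 2 points per dose, and between 1.8 and 3.8 points over the study depending on how far blank fields recur in the same infants.

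The consequence is limited to descriptive 'Any' counts for solicited events, and possibly the combined row for at least one solicited or unsolicited event. Grade rows and the confirmatory immunogenicity tests are unaffected. It should be fixed because it concerns a secondary endpoint and the same data can give two answers.

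**What to change.** Before unblinding, reword the third rule of SAP 6.2.4.2. A missing daily recording should count in 'Any' only when CEOCCUR is yes; an infant with a blank CEOCCUR should count only if a grade of 1 or more is recorded. This brings the paragraph into line with the numerator table, SAP 4.1.2 and protocol 9.4.1.2. It costs one reworded paragraph, with no protocol amendment, no new data and no extra table.

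If the sponsor does intend the third rule, declare it in SAP 4.8 as a departure from protocol 9.4.1.2, and change the 'Any' row of the numerator table and SAP 4.1.2 to match. That costs three SAP edits instead of one.

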**Table 6      Intensity scales for solicited AEs – Attribution for codes for Diarrhea, Vomiting and Fever**

Event	Infant		
	Intensity grade (collected or measured)	Intensity grade (code attributed)	Parameter
Loss of appetite	0	0	Appetite as usual
	1	1	Eating less than usual/no effect on normal activity
	2	2	Eating less than usual/interferes with normal activity
	3	3	Not eating at all
Irritability/Fussiness	0	0	Behavior as usual
	1	1	Crying more than usual/no effect on normal activity
	2	2	Crying more than usual/interferes with normal activity
	3	3	Crying that cannot be comforted/prevents normal activity
Cough/runny nose	0	0	Normal
	1	1	Cough/runny nose which is easily tolerated
	2	2	Cough/runny nose which interferes with daily activity
	3	3	Cough/runny nose which prevents daily activity
Diarrhea	looser than normal stools/day	0	Normal (0-2 looser than normal stools/day)
		1	3 looser than normal stools/day
		2	4-5 looser than normal stools/day
		3	≥ 6 looser than normal stools/day
Vomiting	episodes of vomiting/day	0	Normal (no emesis)
		1	1 episode of vomiting/day
		2	2 episodes of vomiting/day
		3	≥3 episodes of vomiting/day
Fever †	Axillary Temperature (°C)	0	Normal (< 37.5°C)
		1	37.5°C – < 38.0°C
		2	38.0°C – < 39.5°C
		3	≥ 39.5°C
		4	≥ 39.5°C, lasts more than 5 consecutive days

†Axilla is the preferred route to measure temperature in China. If temperature is collected by other routes, the following conversion will be applied:

- Axillary temperature = oral temperature - 0.2°C;
- Axillary temperature = rectal temperature - 0.3°C.

The following table shows how participants contribute to each category for a specific solicited AE over the Day X to Day Y post-vaccination period:

Solicited AE category	Participants included in the calculation of the numerator
Any	All participants with at least 1 occurrence of the solicited AE at grade 1, grade 2, grade 3 or grade 4 between Day X and Day Y or with the solicited AE marked as present and at least 1 missing daily recording between Day X and Day Y
At least grade 1	All participants with at least 1 occurrence of the solicited AE at grade 1, grade 2, grade 3 or grade 4 between Day X and Day Y
At least grade 2	All participants with at least 1 occurrence of the solicited AE at grade 2, grade 3 or grade 4 between Day X and Day Y
At least grade 3	All participants with at least 1 occurrence of the solicited AE at grade 3 or grade 4 between Day X and Day Y

#### 6.2.4.3. Unsolicited adverse events

Unsolicited AE summaries will include unsolicited AEs and SAEs. Solicited events collected within the Day 1 -14 assessment period will be reported in the clinical event (CE) domain while unsolicited events will be reported in the AE domain. Following CBER's request to comply with the CDISC Vaccines Therapeutic Area Guide, solicited events that continue beyond the assessment period will also be reported in the AE domain. These solicited events will not be included in the summaries of unsolicited AEs but will be reported separately.

Missing severity, relationship with study vaccine, and outcome of unsolicited adverse events will not be replaced and will appear as 'UNKNOWN' in all statistical output.

#### 6.2.5. Age at vaccination in weeks

Age at vaccination will be displayed in weeks. It will be calculated as the number of complete weeks between the date of birth (DOB) and the date of vaccination. For example:

DOB = 10JUN2019, Date of vaccination = 28JUL2019 -> Age = 6 weeks

DOB = 10JUN2019, Date of vaccination = 29JUL2019 -> Age = 7 weeks

Incomplete birthdate will follow the general imputation for incomplete date (refer to Section 6.2.3).

#### 6.2.6. Onset day

The onset day for an event (e.g. AE, medication, vaccination) is the number of days between the last study vaccination and the start date of the event. This is 1 for an event occurring on the same day as a vaccination (and reported as starting after vaccination).

### **6.2.7. Counting rules for combining solicited and unsolicited adverse events**

For output combining solicited and unsolicited adverse events, all serious adverse events will be considered general events since the administration site flag is not included in the expedited adverse event case report form (CRF) pages.

Multiple events with the same preferred term which start on the same day are counted as only 1 occurrence.

### **6.2.8. Counting rules for occurrences of solicited adverse events**

When the occurrences of solicited adverse events are summarized, each event recorded as having occurred during a specific period will be counted as only 1 occurrence regardless of the number of days on which it occurs.

### **6.2.9. Immunogenicity data**

- In general, the assay cut-off is the value under which there is no quantifiable result available. For an assay with a specific ‘assay cut\_off’, the numerical immunogenicity result is derived from a character field (IS.ISSTRES):
  - if ISSTRES is ‘NEG’ or ‘-’ or ‘(-)’, numeric result= assay cut\_off/2,
  - if ISSTRES is ‘POS’ or ‘+’ or ‘(+)’, numeric result = assay cut\_off,
  - if ISSTRES is ‘< value’ and value<=assay cut\_off, numeric result =assay cut\_off/2,
  - if ISSTRES is ‘< value’ and value>assay cut\_off, numeric result =value,
  - if ISSTRES is ‘> value’ and value<assay cut\_off, numeric result =assay cut\_off/2,
  - if ISSTRES is ‘> value’ and value>=assay cut\_off, numeric result =value,
  - if ISSTRES is ‘<= value’ or ‘>= value’ and value<assay cut\_off, numeric result =assay cut\_off/2,
  - if ISSTRES is ‘<= value’ or ‘>= value’ and value>=assay cut\_off, numeric result =value,
  - if ISSTRES is a value < assay cut\_off, numeric result = assay cut\_off/2,
  - if ISSTRES is a value >= assay cut\_off, numeric result = ISSTRES
  - else numeric result is left blank.

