## 4. STATISTICAL ANALYSES

### 4.1. General Considerations

#### 4.1.1. Immunogenicity

- Anti-RV IgA Ab concentrations below the assay cut-off will be given an arbitrary value of half the assay cut-off for the purpose of GMC calculation.
- The GMC calculations will be performed by taking the anti-log of the mean of the log concentration transformations.
- A participant is considered seronegative when the Anti-RV IgA Ab concentration is < 20 U/mL and seropositive when  $\geq 20$  U/mL.
- Seroconversion is defined as the percentage of participants who were initially seronegative (i.e., prior the first dose of *Rotarix*) and developed anti-RV IgA Ab concentration  $\geq 20$  U/mL at Visit 3 (1 month post Dose 2).
- For a given participant and a given immunogenicity measurement time point, missing or non-evaluable measurements will not be replaced.

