1080	Vaccine temperature deviation: Participants who have received a vaccine which had a temperature deviation qualified as inappropriate for use by Quality Assurance.
1090	Expired vaccine administered: Participants who received an expired vaccine

Code	Decode: Condition under which the code is used
2010	Protocol violation linked to the inclusion/exclusion criteria: Ineligible participants who was vaccinated (Refer to protocol Section 5 "Study population" for the exhaustive list of inclusion/exclusion criteria).
2020	Anti-RV IgA antibody concentration at pre-vaccination above or equal to 20 U/mL or initially unknown antibody status
2040	Administration of any medication from day 1 to the Visit 3 blood sample which is forbidden by the protocol (see Section 5.2 from the protocol)
2070	Concomitant infection not related to the vaccine which may influence immune response => who have concomitant infection up to Visit 3 blood sample, which may influence the immune system namely RV gastroenteritis, immunosuppressive or immunodeficient conditions identified before Visit 3.
2080	Non-compliance with vaccination schedule (including wrong and unknown dates): Participants who did not comply with the interval for dose 2 (Dose 2 should be between 28-48 days after Dose 1 i.e. Dose 2 date – Dose 1 date should be between 28-48 days).
2090	Non-compliance with the blood sampling schedule (including wrong and unknown dates) => Blood sample not collected within 28 days-48 days after the corresponding intervention
2100	Serological results not available post dose
2120	Obvious incoherence/abnormality or error in data

\* Forced randomization: In case of supplies shortage for the next assigned vaccine according to the randomization schedule at the clinical site, the randomization system will use the forced randomization procedure in order to continue to enrol and vaccinate participants. The system moves seamlessly to the next treatment/randomization number for which vaccine supplies are available. The site will not be aware of the forced randomization event.

\*Manual randomization: In case the randomization system is unavailable, the investigator has the option to perform randomization by selecting supplies available at the site according to a pre-defined rule. In case the randomization system is available, a vaccine different from the randomized treatment may have been administered at dose 1.

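### SAP 6.2.9 records a Visit 3 result known only to lie below a bound as if it equalled that bound, so it can count as a response; if such results occur, the rule favours non-inferiority

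*SAP*

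**What the plan says.** SAP 6.2.9 derives the numeric immunogenicity result from a character field. It describes the cut-off only in words: "In general, the assay cut-off is the value under which there is no quantifiable result available". No figure in U/mL is given there. Four of its lines matter here:

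- For a strict upper bound above the cut-off: "if ISSTRES is ‘< value’ and value>assay cut\_off, numeric result =value".
- For non-strict bounds at or above the cut-off: "if ISSTRES is ‘<= value’ or ‘>= value’ and value>=assay cut\_off, numeric result =value".
- For a strict lower bound below the cut-off: "if ISSTRES is ‘> value’ and value<assay cut\_off, numeric result =assay cut\_off/2".
- Non-strict bounds (`<=` or `>=`) below the cut-off are also set to half the cut-off.

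SAP 4.1.1 then classifies by concentration alone. "A participant is considered seronegative when the Anti-RV IgA Ab concentration is < 20 U/mL and seropositive when" it is at least 20 U/mL. "Seroconversion is defined as the percentage of participants who were initially seronegative" and reached at least 20 U/mL at Visit 3. The first secondary endpoint (SAP 1.1) counts concentrations of at least 90 U/mL. SAP 4.1.1 also says that "missing or non-evaluable measurements will not be replaced".

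For PPS entry, code 2020 in SAP 6.1.3 removes infants with "Anti-RV IgA antibody concentration at pre-vaccination above or equal to 20 U/mL or initially unknown antibody status". Code 2100 covers post-dose results that are not available. It does not mention a post-dose result that is available but indeterminate.

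**The concern.** A report of `<40` gives an upper bound and nothing more. Using the bound as the measurement turns an infant of unknown status into a responder. For `<90` on the ≥ 90 U/mL endpoint the status is not even unknown: the laboratory has said the value is below 90, and the rule counts it as at or above 90.

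The derived number feeds both primary endpoints and the first secondary endpoint. In a non-inferiority trial, error that makes the arms look alike helps the claim. Counting some non-responders as responders at the same rate in both arms does that, because the arm with more non-responders gains more false responses. The margin is -10 percentage points and seroconversion comes first in the hierarchy (SAP 2 and 2.1).

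**Working it through.** **Step 1. The rule applied literally.** Take the cut-off as 20 U/mL, the seronegativity threshold in SAP 4.1.1. This is an assumption.

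| Reported | Numeric result | ≥ 20 U/mL? | ≥ 90 U/mL? |
|---|---|---|---|
| `<20` | 10 | no | no |
| `<=20` | 20 | yes | no |
| `<40` | 40 | yes | no |
| `<90` | 90 | yes | yes |
| `<100` | 100 | yes | yes |
| `>10` | 10 | no | no |

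A less informative report (`<40` instead of `<20`) becomes a positive response.

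**Step 2. The plan's own power as a check on the set-up.** Inputs from SAP 5: 70% vs 67.8%, 750 per arm, margin 10 points, one-sided 0.025.

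- SE = √(0.70×0.30/750 + 0.678×0.322/750) = 0.0239.
- Power = Φ((0.10 − 0.022)/0.0239 − 1.96) = 90.4%, or 90.5% with the Miettinen-Nurminen restricted variance. The SAP states 90%.
- For ≥ 90 U/mL (45.7% vs 43.5%), the restricted-variance calculation gives 86.2%, as stated.

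These figures are not in dispute.

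**Step 3. One-sided error at the margin under the rule.** Let q be the share of Visit 3 samples, equal in both arms, run at a lower limit raised to 40 U/mL. The documents give no value for q. Every such sample counts as ≥ 20: those truly below 40 are set to 40, and the rest are measured at 40 or more. The observed rate is therefore (1 − q)p + q, and the difference is −10(1 − q) points. With true rates of 70% vs 60%, error = Φ(−1.96 + 0.10q/SE).

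| q | Observed rates | Difference | SE | One-sided error |
|---|---|---|---|---|
| 0 | 70.0% vs 60.0% | −10.0 | 0.0245 | 2.5% |
| 1% | 70.3% vs 60.4% | −9.9 | 0.0244 | 2.75% |
| 5% | 71.5% vs 62.0% | −9.5 | 0.0242 | 4.0% |
| 10% | 73.0% vs 64.0% | −9.0 | 0.0239 | 6.2% |

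For ≥ 90 U/mL (45.7% vs 35.7%, lower limit raised to 90 or more) the error is 2.74% at q = 1% and 3.9% at q = 5%.

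**Step 4. GMC.** If 1% of an arm's results should stand at 10 U/mL but are set to 40, that arm's GMC is multiplied by (40/10)^0.01 = 1.014. Set to 200, the factor is 20^0.01 = 1.030. Equal factors cancel in the ratio. Unequal numbers of affected infants do not.

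**Step 5. Comparing repairs for seroconversion.** This needs the rate above 40 U/mL. Interpolate on the log scale between 70% at 20 and 45.7% at 90: ln 2/ln 4.5 = 0.461, so 70 − 0.461×24.3 = 58.8%. Assume the test arm is 10 points lower throughout, giving 48.8%.

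- *`<40` treated as missing.* The rate is ((1−q)p + q·p40)/((1−q) + q·p40). At q = 10% this gives 71.8% vs 62.1%. One-sided error is about 2.55%, 2.75% and 3.1% for q = 1%, 5% and 10%. Some bias remains because only samples below 40 are dropped, and most of those are non-responders.
- *`<40` counted as a non-responder.* The rate is (1−q)p + q·p40. The difference stays at −10 points and the error at 2.5%. This relies on the assumed 10-point gap at 40 U/mL. With an 8-point gap and q = 5%, the difference would be −9.9 points and the error about 2.75%.

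**The case against.** The strongest reply is that the line may never be used. SAP 6.2.9 is a generic list that also covers results reported as positive or negative. The trial's only assay is a quantitative ELISA read from a four-parameter curve (Protocol 10.2). That description mentions serum dilutions but no sample-specific raised lower limit. About 2 mL of blood serves a single assay, so short volume is an unlikely cause. This stands. A reader might infer from the written rule that such results are expected, or that the trial's type I error is in fact inflated. The documents support neither.

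A reader might also infer harm at Visit 1, because `<40` at baseline makes an infant look seropositive. For the PPS this is immaterial: code 2020 also removes unknown baseline status, so the infant leaves either way.

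Nor are the `<=` and `>=` lines wrong throughout. `<=` below the cut-off is rightly seronegative, and `>=` at or above it is rightly seropositive. The mirror case, a `>` result below the cut-off, is hard to reach given how 6.2.9 describes the cut-off.

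It can be said that other provisions catch the problem: non-evaluable results are not replaced, and code 2120 allows exclusion for obvious data errors. That does not hold. A valid `<40` is not an error, and 6.2.9 gives it a number, so it is never treated as non-evaluable. The ES repeat in SAP 4.2.3 and 4.3.3 uses the same derived values. The SAP does not say outright that the binary endpoints use the derived number, but it offers no other rule.

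**Conclusion.** The rule is wrong as written for Visit 3 results reported as `<` a value above the cut-off, or `<=` a value at or above it. With a 20 U/mL cut-off, the first produces seroconverters of unknown status, and `<90` is misclassified outright on the ≥ 90 U/mL endpoint. A cut-off below 20 would narrow the range: a bound between that cut-off and 20 would not make an infant seropositive.

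The direction favours non-inferiority when such results are balanced between arms. The size depends on a frequency that the documents do not give: nil if none occur, and a one-sided error of about 2.75% at q = 1% or 4.0% at q = 5%. The 5% case means about 38 infants per arm (0.05 × 750) run at a raised limit, and nothing in the documents suggests that many. The laboratory is blinded (Protocol 6.3.4), so there is no reason to expect a bias confined to one arm. This is a rule to correct before unblinding. It is not evidence that the trial's conclusion is unsafe.

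**What to change.** Amend SAP 6.2.9 and the derivation code as follows.

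- **Binary endpoints at Visit 3:** classify by the bound. `<` a value of 90 or less, or `<=` a value below 90, counts as below 90 U/mL. Where a `<` or `<=` result leaves the 20 or 90 U/mL status open, do not count it as a responder for that endpoint. Add a sensitivity analysis that treats it as non-evaluable.
- **GMC:** do not use the upper bound as the measured concentration. Treat the result as non-evaluable, with a sensitivity analysis at half the cut-off.
- **Lower bounds below the cut-off** (`>` or `>=`): treat as non-evaluable instead of half the cut-off.
- **Leave unchanged** `<=` below the cut-off and `>=` at or above it.
- **State the assay cut-off in U/mL**, and tabulate all such results by arm.

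The cost is a few lines of SAP text and code. A handful of results, if any, become non-responders or leave the GMC. Under the interpolation in Step 5, seroconversion power at 70% vs 67.8% stays at about 90% (unpooled formula) even at q = 5%.
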